3.2 Exclusion Criteria

Patients with the following conditions are not eligible to participate in this trial:

- Pregnant women or women of childbearing potential without adequate contraception. Contraception, which can include abstinence, is required since the last menstrual period until completion of SRS.
- Evidence of pneumothorax
 - Untreated pneumothorax risks tension pneumothorax during ascent in HBO chamber
- COPD with CO₂ retention
 - Such patients can develop respiratory depression as HBO reduces their hypoxic drive
- Uncontrolled seizure disorder
 - Note that patients on adequate antiepileptic medications may receive HBO
- Claustrophobia resistant to medication
 - Pre-medication with anxiolytics is generally sufficient for almost all anxious patients undergoing HBO treatment
- History of middle ear surgery
 - Failure to equalize pressure in the middle ear can cause displacement of middle ear structures with consequent hearing loss
 - To clarify: placement of a tympanostomy tube is not a contraindication to HBO, and in fact may improve tolerability of the procedure
- History of bleomycin administration
 - HBO can exacerbate interstitial pneumonitis in such patients
- Current cis-platinum chemotherapy (i.e. therapeutic levels in the bloodstream at the time of HBO therapy)
 - HBO can increase cytotoxicity of cis-platinum
- Uncontrolled high blood pressure
 - HBO can increase systemic vascular resistance
- Unstable angina or myocardial infarction within the previous 3 months
 - Increased afterload due to HBO can increase myocardial workload
- Cardiac EF ≤ 35%
 - Pulmonary edema can arise with HBO in certain patients with severe heart failure
 - In patients with prior history of CHF, subsequent echocardiogram and ECG are required to establish EF>35%
- Treatment with disulfiram

- Disulfiram inhibits superoxide dismutase and is not approved for use concomitantly with hyperbaric oxygen therapy
- Active drug/alcohol dependence or abuse
- Lack of adequate social support structures, e.g. homelessness
- Tumors with potential confounding results on serum marker studies
 - Small cell (neuroendocrine) carcinomas
 - Carcinoid tumors

3.3 *Subject Recruitment and Screening*

Subjects will be recruited from patients who are potential candidates for SRS treatment at DHMC for brain metastases. Such patients are referred to radiation oncology by practitioners at DHMC and by physicians at outlying hospitals.

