For the secondary endpoints, using Cox proportional hazards models, and Kaplan-Meier survival statistics, the overall group of 20 will be analyzed for event-free survival and compared against a matched set of patients from our institution (see below for methodology). This match will be based on tumor size, resection status, and histology-specific graded prognostic assessment (GPA). The GPA is a validated, widely accepted prognostic scale predictive of survival for patients presenting with brain metastases. Diagnosis-specific GPA calculation is based on published criteria including tumor histology, presence of systemic metastases, number of brain metastases, age, performance status, and breast-cancer specific molecular markers [29-31]. Further demographic and treatment data will also be collected, including: gender, subtotal resection versus gross total resection (if tumor resected), tumor diameter (prior to first treatment, whether surgery or SRS), SRS target volume (PTV), and prescribed dose to the PTV. The secondary outcome variables will be the first occurrence of the event of interest and also the time until the first occurrence of the event of interest. These events include: intracranial recurrence at SRS site, intracranial recurrence at a distant site, whole brain XRT, second SRS (classified as either local or distant), third SRS (classified as local or distant), radionecrosis at the SRS site, and death.

A retrospective database pertaining to Dartmouth-Hitchcock's experience with stereotactic radiosurgery in the treatment of brain metastases is being collected through Study 00030625 (PI [name]). Pertinent matching variables, along with demographic variables, treatment variables, and outcome variables for the control population are available on 00030625. The matching variables (histology, lesion size, resection status, and calculated GPA) will be used to identify a control population in the Study 00030625 that match 1:1 against the D12129 enrolled patient population.

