Specifically, patients with similar tumor histologies will be matched against histologies found in the D12129 patient population, falling into one of six categories: (1) non-small cell lung cancer, (2) melanoma, (3) breast cancer, (4) renal cell cancer, (5) GI cancers, and (5) other histologies. Once a histologic match is identified, the patient is then matched by resection status (either unresected or resected). The third matching variable is then GPA. If an exact GPA match is not available in the 000030625 data base, then a patient with a higher GPA will be selected, with the control patient's GPA as near as possible to that of the corresponding D12129 patient (thereby, if anything, biasing the survival outcome data slightly against the D12129 data set). Lastly, the fourth matching variable is tumor size (i.e. maximum tumor diameter) at time of treatment (a categorical variable, either below or above 2.0 cm). If an exact match for the fourth variable is not available in the 000030625 data base, then size will be matched as closely as possible to the 2.0 cm cut-off from those patients available in this historical database. These

matching patients identified in 000030625 data base will serve as the control group for the D12129 study.

Once the control group patients have been selected, their data will be extracted from the 000030625 database in de-identified form. These data will be reviewed by an “honest broker” to assure proper de-identification and HIPAA compliance. These de-identified control group data will then be merged with the D12129 dataset. Analysis of this combined data base then will allow comparison of HBO-treated and control patients in terms of event-specific outcome parameters, with events including: death, local intracranial recurrence, distant intracranial recurrence, whole brain radiation therapy, and repeat SRS (either local or distant).

Exploratory variables will include QOL data and tumor markers. Comparisons for change in markers before versus after HBO-SRS treatment will be performed for the entire group of twenty patients. Also comparisons will be performed for subgroups (including comparisons of those with resections versus those without, and of those above 2.0 cm diameter versus those below).

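### Section 6.1 does not apply the trial's eligibility criteria to the control pool, so controls may include patients who could not have entered D12129

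*Combined protocol and SAP*

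**What the plan says.** Section 6.1 names the source of controls: "A retrospective database pertaining to Dartmouth-Hitchcock's experience with stereotactic radiosurgery in the treatment of brain metastases is being collected through Study 00030625". Selection is then described in order: histology group, resection status, GPA, and size on either side of 2.0 cm. The four variables are restated as the whole basis of selection: "The matching variables (histology, lesion size, resection status, and calculated GPA) will be used to identify a control population in the Study 00030625". The pairing is to "match 1:1 against the D12129 enrolled patient population", and the process ends with "matching patients identified in 000030625 data base will serve as the control group for the D12129 study".

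On GPA, the same section says: "Diagnosis-specific GPA calculation is based on published criteria including tumor histology, presence of systemic metastases, number of brain metastases, age, performance status", and adds molecular markers for breast cancer. If no exact GPA match exists, a control with a higher score is taken, "thereby, if anything, biasing the survival outcome data slightly against the D12129 data set".

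Trial patients pass a further screen. Section 3.1 requires KPS of at least 70 and a lesion no larger than 5.0 cm. Section 3.2 removes patients with, among other things, hypercapnic COPD, pneumothorax, a low ejection fraction, a recent infarction or unstable angina, uncontrolled hypertension or seizures, and active substance dependence. It also lists "Lack of adequate social support structures, e.g. homelessness" and "Tumors with potential confounding results on serum marker studies", the latter meaning small cell and carcinoid tumors. No section applies these criteria to the controls.

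**The concern.** The HBO-SRS group is filtered for fitness to enter a pressure chamber. The control group, as the plan is written, is not. Matching removes this difference only where the matching variables carry the same information, and for several exclusions they do not.

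Section 2.1.1 aims to show that outcomes are non-inferior to historical controls, and Section 6.1 lists death among the events. If some controls have a worse outlook for reasons that would have barred them from the trial, HBO-SRS looks better on survival than it should, and a real harm could be partly hidden. A non-inferiority comparison is least protected against error in that direction, and the plan states no margin against which a given shift could be called tolerable.

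**Working it through.** **1. Eligibility set against the matching variables**

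| Trial criterion (3.1, 3.2) | Covered by matching in 6.1? |
|---|---|
| KPS at least 70 | Partly. Performance status is one component of GPA, but a matching composite score does not guarantee KPS of at least 70 |
| Lesion up to 5.0 cm | No. The upper size category has no cap |
| No small cell or carcinoid | Not explicitly. The residual histology group does not bar them |
| Cardiac, pulmonary and blood-pressure exclusions | No |
| Uncontrolled seizures | No |
| Substance dependence, lack of social support | No |

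Following 6.1 to the letter can therefore select a control who fails 3.1 or 3.2.

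**2. The plan's own figure for this comparison**

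Section 6.2 gives a detectable relative risk of 0.39 (20 per group, control median 6 months, one-sided 0.05, power 0.80). Freedman's formula gives (1.39/0.61)² × (1.645 + 0.842)² = 5.19 × 6.18 = 32.1, rounded up to 33 events. Expected events with 24 months of follow-up are 20 × (0.9375 + 0.661) = 32.0, giving power 0.799. The figure reproduces. It concerns random error only, and neither the problem nor the fix changes it.

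**3. Illustration for survival**

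From the documents: 52.5% alive at 1 year (Table 1), so λ = −ln(0.525)/12 = 0.0537 per month. Assumed, because the documents do not give them: a fraction f of controls is ineligible with h times the death hazard, hazards are constant, and follow-up is censored at 24 months.

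- Control survival: S_C(t) = (1 − f)·exp(−λt) + f·exp(−hλt).
- HBO-SRS survival: S_T(t) = exp(−θλt), where θ is the true hazard ratio (HR).
- The large-sample Cox HR is e^β, where β solves ∫₀²⁴ [d_T(1 − p) − d_C·p] dt = 0. Here d is each arm's death density and p = e^β·S_T/(e^β·S_T + S_C).

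| f | θ = 1.0, h = 1.5 | θ = 1.0, h = 2 | θ = 1.3, h = 1.5 | θ = 1.3, h = 2 |
|---|---|---|---|---|
| 2% | 0.99 | 0.99 | 1.29 | 1.28 |
| 5% | 0.98 | 0.97 | 1.27 | 1.26 |
| 10% | 0.96 | 0.94 | 1.25 | 1.22 |
| 20% | 0.92 | 0.88 | 1.20 | 1.14 |
| 30% | 0.89 | 0.82 | 1.15 | 1.07 |

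A hand check at f = 30%, h = 2: the hazard ratio at time zero is 1/(0.7 + 0.3 × 2) = 0.77. It drifts towards 1 as the higher-risk controls die, and the Cox value over 24 months is 0.82.

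**4. Illustration for crude incidence of local recurrence**

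Table 1 gives 85.5% free of local recurrence at 1 year, so μ = −ln(0.855)/12 = 0.01305 per month, assumed the same in all controls. Observed recurrence by 24 months, with death hazard kλ, is μ/(μ + kλ) × [1 − exp(−24(μ + kλ))].

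- k = 1: 0.1956 × 0.7985 = 15.6%.
- k = 2: 0.1084 × 0.9445 = 10.2%.
- Controls with 30% at k = 2: 0.7 × 15.6 + 0.3 × 10.2 = 14.0%.

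On this measure, unfit controls show fewer recurrences, so HBO-SRS would look worse.

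**5. Shift against precision**

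Expected deaths by 24 months are 40 × (1 − 0.525²) = 29.0. SE(log HR) ≈ 2/√29 = 0.37, so a 95% interval spans a factor of exp(1.96 × 0.37) ≈ 2.1 either way. The largest shift in the table, −ln(0.82) ≈ 0.19, is about half a standard error.

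**The case against.** Several points on the other side are sound.

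- **The plan already leans towards fitter controls in one place.** GPA carries age and performance status, and an inexact GPA match goes to a higher-scoring control. That narrows the KPS gap. It does nothing for the cardiac, pulmonary, seizure or social exclusions.
- **Entry of ineligible controls is possible, not shown.** The selection criteria of Study 00030625 are not in these documents. The lung category is non-small cell, histologies are matched to those found among trial patients, Section 14.5.2 calls brain metastasis from carcinoid rare, and the SRS dose table stops at 5.0 cm. Some of these routes may be empty in practice.
- **The shares and hazards above have no anchor in the documents.** At a 2% to 5% ineligible share the effect is negligible. Table 1 also comes from 49 resected patients, whereas half the planned trial patients have intact lesions.
- **The comparison is imprecise anyway.** It is secondary in a 20-patient feasibility study. That limits the weight of the point, but a wide interval does not excuse an avoidable bias.

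A reader might also infer that Section 6.1 claims all matching bias runs against HBO-SRS. It does not. The remark "thereby, if anything, biasing the survival outcome data slightly against the D12129 data set" qualifies only the higher-GPA fallback and only survival data, and for that rule it is reasonable.

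**Conclusion.** The concern holds in limited form. The written procedure can admit controls who could not have entered the trial, and the matching variables close only part of the gap. For survival and composites that include death, the likely direction favours HBO-SRS. For crude incidence of non-fatal events, it can be the reverse.

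The size is unknown. Under the assumptions shown (ineligible share 2% to 30%, twice the death hazard, constant hazards from Table 1, 24 months), a true HR of 1.0 would be estimated at about 0.99 to 0.82.

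Three stronger readings are tempting but unsupported: that ineligible controls are certain to be selected, that this bias outweighs the higher-GPA rule, and that it favours HBO-SRS on every endpoint. The documents size neither bias, and step 4 contradicts the last reading. The change is worth making because the comparison supports a non-inferiority claim and the remedy is cheap.

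**What to change.** In Section 6.1:

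1. Before matching, restrict the 00030625 pool to patients who meet those 3.1 and 3.2 criteria that can be checked from database fields: KPS, lesion size up to 5.0 cm, and absence of small cell or carcinoid histology.
2. Before the honest-broker de-identification, have someone blind to outcome check each provisionally selected control's record for documented HBO exclusions. Take the next-best match when one fails.
3. List the criteria that cannot be verified retrospectively (possibly CO2 retention, ejection fraction and social support) and report how many controls were excluded and why.
4. Keep the remark on the higher-GPA rule, and add that it does not describe the net bias of the comparison.

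The cost is a paragraph of text and a review of at least 20 records, plus one more for each control that fails, possibly with extra access under Study 00030625. The pool will be smaller and some matches less exact, although the center treats about 80 to 100 SRS patients a year. No additional trial patients are needed, and the Section 6.2 calculation does not change.

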6.1 Statistical Methods

For the primary outcome variable of feasibility, the twenty evaluable patients will be analyzed on the basis of the amount of time required from leaving the HBO chamber to beginning SRS for the target lesion (T1).

The goal for each patient (as discussed in Section 2.2) is for T1 to be no greater than 15 minutes. In a Phase I trial of HBO treatment in coordination with fully fractionated head-neck cancer XRT, DHMC established a track-record of an average of only eight minutes from time of leaving the HBO chamber to “beam on” for this patient group [22]. However, set-up for SRS treatment is more complex, involving placement of a head-frame and performance of a CT-scan prior to SRS treatment. These may extend the time interval required for patient set-up after leaving the HBO chamber.

We anticipate a learning curve for the team members of this study. Therefore, stopping rules are as outlined in Section 7.4: no more than 20% of first ten patients treated within

30 minutes of HBO; and no more than 33% of first fifteen patients treated within 30 minutes of HBO.

The primary endpoint of feasibility is defined as having been achieved if more than 50% of the 20 evaluable patients start SRS treatment within 30 minutes of leaving the HBO tank: in other words, T1 is ≤ 30 minutes for $>50\%$ of evaluable patients.

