14.1 Table summarizing study procedures/flowchart

Visit sequence	Type	Description	Data/Activities
#1	Initial consultation visit	Consults with radiation oncology and neurosurgery	H+P** Protocol screening (check inclusion/exclusion criteria, including pathology/radiology) Protocol consent Bloodwork (CBC, CMP, pregnancy test if indicated) Optional biomarker blood draw Chest imaging if indicated (per section 3.1)
#2	Pre-treatment visit	HBO and SRS preparation	Patient familiarized with HBO technique ("dry run" through the HBO chamber) RT-planning brain MRI VisionRT open face mask fitting CT-based simulation for SRS planning
#3	SRS treatment visit	HBO and SRS treatments	HBO SRS to brain metastases (beam-on goal within 15 minutes after leaving HBO decompression)
#4+	Follow-up visit	Follow-up visits – the first 4-6 weeks after SRS, then every 3 months for two years, then every 4 months for one year, then every 6 months for two years, then annually. Individuals in the substudy for biomarkers will have an additional follow-up the day after the SRS treatment visit.	H+P** Brain MRI Bloodwork at first follow-up visit (CBC, CMP) Optional biomarker blood draw

** Note: All history/physical exam evaluations will include vital signs, performance status, neurological exam, mini-mental status exam, and QOL assessments (EORTC Quality of Life C-30 and BCM20).

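### Controls for the secondary comparison are chosen without regard to SRS date, so change in practice over time cannot be separated from an HBO effect

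*Combined protocol and SAP*

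**What the plan says.** Section 2.1.1 makes non-inferiority to historical controls the secondary objective. Section 6.1 of the combined protocol and SAP names the source: "A retrospective database pertaining to Dartmouth-Hitchcock's experience with stereotactic radiosurgery in the treatment of brain metastases is being collected through Study 00030625". It gives no start or end date for that database. Selection rests on four variables: "The matching variables (histology, lesion size, resection status, and calculated GPA) will be used to identify a control population in the Study 00030625".

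Controls are to "match 1:1 against the D12129 enrolled patient population". The rule is sequential: histology category, then resection status, then GPA, with a fallback to the nearest higher GPA. It ends: "Lastly, the fourth matching variable is tumor size (i.e. maximum tumor diameter) at time of treatment", dichotomized at 2.0 cm and with its own fallback. If several database patients fit equally well, the text does not say which to take.

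Other variables are recorded: "Further demographic and treatment data will also be collected, including: gender, subtotal resection versus gross total resection", together with diameter, PTV and prescribed dose. Year of treatment, set-up and systemic therapy are not in that list. Cox models are named without covariates. The events to be compared include "whole brain XRT, second SRS (classified as either local or distant), third SRS (classified as local or distant", alongside local and distant recurrence, radionecrosis and death.

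**The concern.** A historical comparison assumes that, apart from the study treatment, controls were managed as the trial patients are. Matching on histology, resection, GPA and size addresses who the patients were. It does not address when they were treated. GPA, as 6.1 describes it, is built from histology, systemic metastases, number of brain metastases, age, performance status and breast-cancer markers, and none of these carries treatment era.

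WBRT and repeat SRS are the most exposed. They happen because a clinician chooses them, and the protocol sets no criteria for that choice in trial patients or controls. A shift in local preference would change their frequency with no change in tumor biology. Recurrence and survival can also move with systemic therapy and set-up. Drift that favors later patients could hide harm from HBO, and drift the other way could create an apparent harm. The only selection bias that 6.1 discusses is the one from taking a higher-GPA control.

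**Working it through.** **1. Where date could enter the plan.**
- Candidate pool: the whole database, no date limit.
- Matching variables: four, none of them date.
- Fallbacks: for GPA and size only.
- Choice among equal matches: not stated.
- Model covariates: none named.

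Following 6.1 as written therefore allows a control from any period the database covers.

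**2. The plan's own figure, used to fix an event count.** Section 6.2 gives a control median of 6 months, one-sided 0.05, power 0.80 and a detectable relative risk of 0.39, with 20 patients against 20 controls. The Freedman formula requires ((1 + 0.39)/(1 − 0.39))² × (1.645 + 0.842)² = 5.19 × 6.18 ≈ 32.1, that is 33 events. Under exponential survival with 24 months' follow-up (Section 5.4), the expected events are 20 × (1 − 2⁻⁴) = 18.75 in controls and 20 × (1 − e^(−0.39 × 0.1155 × 24)) ≈ 13.2 in trial patients, about 32 in all, for a power of 0.799. So 0.39 reproduces. It concerns event-free survival and is used here only to set a realistic number of events. The Schoenfeld formula needs 28. With equal hazards, 24 months gives 2 × 18.75 = 37.5, about 38. The range is therefore 28 to 38.

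**3. What drift would do (illustration).** Assume HBO has no effect and drift alone multiplies the hazard in trial patients by δ. δ is not in the documents, so a range is shown. With d events split over two equal groups:

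- chance of a one-sided 0.05 benefit = Φ(√(d/4) × (−ln δ) − 1.645)
- power to detect a true harm of 1.61 (the 61% increase named in 6.2) = Φ(√(d/4) × ln(1.61 δ) − 1.645)

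Example, d = 33 and δ = 0.8: √8.25 = 2.872; 2.872 × 0.223 − 1.645 = −1.004; Φ = 0.158. For harm: 2.872 × ln(1.288) − 1.645 = −0.918; Φ = 0.179.

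| δ | False benefit, d = 28 / 33 / 38 | Power for HR 1.61, d = 28 / 33 / 38 |
|---|---|---|
| 1.0 | 5.0% / 5.0% / 5.0% | 35.0% / 39.1% / 43.0% |
| 0.9 | 8.6% / 9.0% / 9.3% | 25.3% / 28.1% / 30.8% |
| 0.8 | 14.6% / 15.8% / 16.9% | 16.5% / 17.9% / 19.4% |
| 0.7 | 24.2% / 26.8% / 29.3% | 9.2% / 9.7% / 10.1% |

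Drift in the opposite direction gives false signals of harm at the same rates. The calculation treats the groups as independent and uses the log-rank test of 6.2, because no non-inferiority margin is stated from which a false non-inferiority rate could be computed.

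**The case against.** The strongest reply is that this is a 20-patient proof-of-principle study whose primary endpoint, time from chamber to beam-on, uses no controls. The database may cover a short recent period, or its own protocol may restrict dates; neither can be seen here. The scope limit stands. The second point is a possibility, and nothing in 6.1 requires recent controls.

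Four stronger readings are tempting, and the documents do not support them.

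- **That the text shows practice has changed.** Section 6.1 refers to "involving placement of a head-frame and performance of a CT-scan prior to SRS treatment", while 14.1 lists "VisionRT open face mask fitting" and 14.3 allows either device. All of these describe trial patients. They show two set-ups, or an inconsistency, within the trial and say nothing about how controls were treated. Change in salvage practice and systemic therapy is a reasonable inference, not a documented fact.
- **That Table 1 sizes the drift for WBRT.** Its all-subjects column implies 100 − 58.4 = 41.6% with WBRT by one year, which could be set against a lower assumed later rate. That series is of resected lesions, 34 of 49 above 2.0 cm. The trial plans equal numbers above and below 2.0 cm (6.2), and controls are matched on that cut. At a 50:50 mix Table 1 gives (100 + 44.5)/2 = 72.25% free, or 27.75% with WBRT. If later practice were 20–30% (assumption), the hazard ratio would run from ln(0.80)/ln(0.7225) = 0.69 to ln(0.70)/ln(0.7225) = 1.10, so not even the direction is settled. Table 1 also has no rate for intact lesions.
- **That controls close in time exist because the database is still being collected.** A retrospective collection in progress may hold only older treatments.
- **That the pool is ample because the center treats 80–100 SRS patients yearly (6.2).** That count is not stated to be brain metastases or database entries.

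**Conclusion.** The omission is verified: SRS date has no role in selecting or analyzing controls. The supportable conclusion is that drift cannot be separated from an HBO effect in the secondary comparison. A reader might go further and infer that drift is being counted as an HBO benefit; that would need a size and direction the documents do not give. The figures in the table rest on assumed drift, exponential survival and 28 to 38 events. They show only that modest drift would matter at this sample size. WBRT and repeat SRS are the least interpretable of the compared events. The change is worth making because a named objective depends on this comparison and the remedy is cheap. The primary endpoint, the sample size and the stated 0.39 are untouched.

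**What to change.** In 6.1:

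1. Among database patients who match equally on the four variables, take the one whose SRS date is nearest to the trial patient's.
2. Report the SRS dates of both groups, and the set-up where it was recorded.
3. If the database dates allow, also restrict the pool to a recent window stated before controls are selected.
4. State that comparisons of WBRT and repeat SRS are descriptive.
5. Show distant brain recurrence only as a low-precision check for residual bias. With 20 against 20 a null result reassures little, and it would not reveal changes in local set-up or salvage choice.

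An estimate adjusted for SRS year is not proposed: if most controls predate the trial, year is nearly collinear with group and the result would be unstable.

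The cost is a few sentences. SRS date is needed for the time-to-event analyses anyway, and controls are selected before the de-identified extraction, so the rule can be applied at that step. The tie-break costs no match quality. The window would leave somewhat fewer exact matches.
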